8.1 Definitions

Adverse Event

An **adverse event** (AE) is any symptom, sign, illness or experience that develops or worsens in severity during the course of the study. Intercurrent illnesses or injuries should be regarded as adverse events. Abnormal results of diagnostic procedures are considered to be adverse events if the abnormality:

- results in study withdrawal
- is associated with a serious adverse event
- is associated with clinical signs or symptoms
- leads to additional treatment or to further diagnostic tests
- is considered by the investigator to be of clinical significance

Serious Adverse Event

Adverse events are classified as serious or non-serious. A **serious adverse event** is any AE that is:

- fatal

CONFIDENTIAL

This material is the property of the Seattle Children's Research Institute. Do not disclose or use except as authorized in writing by the study sponsor-investigator.

- life-threatening
- requires or prolongs hospital stay
- results in persistent or significant disability or incapacity
- a congenital anomaly or birth defect
- an important medical event

Important medical events are those that may not be immediately life threatening, but are clearly of major clinical significance. They may jeopardize the subject, and may require intervention to prevent one of the other serious outcomes noted above. For example, drug overdose or abuse, a seizure that did not result in in-patient hospitalization or intensive treatment of bronchospasm in an emergency department would typically be considered serious.

All adverse events that do not meet any of the criteria for serious should be regarded as non-serious adverse events.

Adverse Event Reporting Period

The study period during which adverse events must be reported is normally defined as the period from the initiation of any study procedures to the end of the study treatment follow-up. For this study, the study treatment follow-up is defined as 30 days following the last administration of study treatment.

Preexisting Condition

A preexisting condition is one that is present at the start of the study.

General Physical Examination Findings

At screening, any clinically significant abnormality should be recorded as a preexisting condition. At the end of the study, any new clinically significant findings/abnormalities that meet the definition of an adverse event must also be recorded and documented as an adverse event.

Post-study Adverse Event

All unresolved adverse events should be followed by the investigator until the events are resolved, the subject is lost to follow-up, or the adverse event is otherwise explained. At the last scheduled visit, the investigator should instruct each subject to report any subsequent event(s) that the subject, or the subject's personal physician, believes might reasonably be related to participation in this study.

Abnormal Laboratory Values

A clinical laboratory abnormality should be documented as an adverse event if any one of the following conditions is met:

- The laboratory abnormality is not otherwise refuted by a repeat test to confirm the abnormality
- The abnormality suggests a disease and/or organ toxicity
- The abnormality is of a degree that requires active management; e.g. change of dose, discontinuation of the drug, more frequent follow-up assessments, further diagnostic investigation, etc.

Hospitalization, Prolonged Hospitalization or Surgery

Any adverse event that results in hospitalization or prolonged hospitalization should be documented and reported as a serious adverse event unless specifically instructed otherwise in this protocol. Any condition responsible for surgery should be documented as an adverse event if the condition meets the criteria for an adverse event.

Neither the condition, hospitalization, prolonged hospitalization, nor surgery are reported as an adverse event in the following circumstances:

- Hospitalization or prolonged hospitalization for diagnostic or elective surgical procedures for a preexisting condition. Surgery should **not** be reported as an outcome of an adverse event if the purpose of the surgery was elective or diagnostic and the outcome was uneventful.
- Hospitalization or prolonged hospitalization for therapy of the target disease of the study, unless it is a worsening or increase in frequency of hospital admissions as judged by the clinical investigator. (Note: This study population includes a notable proportion of patients requiring hospital readmissions due to refractory IVIG therapy. A clear definition of a *serious adverse event* relating to readmissions will be determined at the Organizational Meeting with the Data Monitoring Committee.)

Expected Adverse Events

The following AEs are expected with Kawasaki Disease and IVIG:

Fever, chills, sore throat, chest tightness, rash, redness of the eyes, vomiting, diarrhea, headache, nausea, irritability, meningismus, anaphylaxis or hypersensitivity, hypotension, rash, skin peeling or desquamation, extremity swelling, coronary arteritis, coronary aneurysms, myocardial infarction, myocarditis, mitral regurgitation, pericarditis, hydropic gall bladder, joint swelling or pain, lymphadenopathy, arrhythmias, blood clots.

Lab abnormalities; elevated CRP and ESR; thrombocytosis, hypoalbuminemia, anemia, pyuria, elevation of liver transaminases.

Additionally, localized redness and swelling at injection site are expected AEs for etanercept. A full list of AEs is included in the Etanercept package insert.

Serious Adverse Events expected are readmission due to recurrent or persistent fever.

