3.2 Secondary Clinical Endpoints

Determine if the safety profile differs between the etanercept treated group and the placebo group.

Secondary safety endpoints will be number of adverse events, serious or otherwise within 30 days of treatment, with specific focus on serious infections, defined as “those requiring hospital admission” for treatment. The latter have been noted in patients receiving much longer courses of etanercept than proposed for this protocol, and for different diseases.

Our study will be the first to evaluate efficacy of Etanercept in reducing inflammation in an acute inflammatory disease in children, as opposed to chronic inflammatory diseases. The acute phase reactant, C-reactive protein, will be followed throughout the study as a laboratory measure of inflammation. We will also determine if etanercept modifies serum concentrations of cytokines, interleukin-3, interleukin-6, and TNF- α .

We propose the largest cohort for study of Etanercept in children performed to date.

Secondary clinical endpoints will be directed to determine if etanercept treatment alters the rate of coronary artery disease defined by z-scores at 2 and 6 weeks after treatment.

We will also determine if etanercept treatment 1) alters development of coronary artery dilation or disease in patients with normal coronaries on initial echocardiogram, 2) promotes healing of coronary artery disease, when apparent on initial echocardiogram, 3) alters treatment course by reducing total number of hospitalization days, and 4) incidence of CRP normalization by 7 days.

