3.3 Dosing

Etanercept or placebo will be administered in three separate doses (0.8 mg/kg subcutaneously, maximum 50 mg) at 1 week intervals with the first dose concurrent with IVIG or within 48 hours of initiating IVIG.

Rationale for extended therapy: Current KD treatment with IVIG and ASA in the United States is based on efficacy comparison with ASA alone⁸. Subsequently, studies showed no difference in efficacy between IVIG (400 mg/kg) given in 4 separate doses on consecutive days versus a single infusion IVIG (2 gm/kg) over 10 hours¹². Nevertheless, data across more than 2 decades show that coronary artery involvement increases during the 2 week period following treatment. Furthermore, refractoriness to IVIG can manifest up to 2 weeks after completion of IVIG. Inoue¹³ et al showed some increased benefit of continuing oral steroids until inflammatory parameters such as CRP normalized. In that study, laboratory studies were performed at least twice weekly. Normalization of CRP level in the placebo group (receiving IVIG and ASA, no corticosteroid) occurred in 9.0 days (median) range 4 to 42 and mean 11.2 ± 6.2 days. These data, along with the their results showing some mild efficacy by more prolonged corticosteroid therapy, strongly support the contention that anti-inflammatory therapy for KD should be extended to near 3 weeks, provided therapy is convenient and low-risk. Accordingly, we will maintain treatment for 3 weeks to cover all patients within this vulnerable period. As our pilot data suggest that Etanercept levels are maintained at a near steady-state by week 2, we will give the final dose at $14 \text{ days} \pm 2$ in order to maintain levels at least 3 weeks.

4 Patient Population and Sample Size

196 study participants will be recruited from the four participating medical center admissions for suspected Kawasaki Disease with IVIG administration. Seattle Children's Hospital is the coordinating site for the study. Most patients will be on the Cardiology or General Medicine Service.

4.1 Inclusion criteria:

Identification of patients with KD:

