5.7.4 Return or Destruction of Study Drug

Study drug that remains at the end of the study will be shipped back to Amgen, Inc or destroyed on site.

At the completion of the study, there will be a final reconciliation of drug shipped, drug consumed, and drug remaining. This reconciliation will be logged on the drug reconciliation form, signed and dated. Any discrepancies noted will be investigated, resolved, and documented prior to return or destruction of unused study drug. Drug destroyed on site will be documented in the study files.

6 Study Procedures

Etanercept 0.8mg/kg (maximum 50 mg) or placebo will be given within 48 hours of initiating IVIG infusion. Randomization will be performed by internal Pharmacy, unblinded (see Pharmacy procedures). Placebo format

CONFIDENTIAL

This material is the property of the Seattle Children's Research Institute. Do not disclose or use except as authorized in writing by the study sponsor-investigator.

will be: Etanercept placebo (Amgen), TMS Lyo, B20 UnLBL 2mL vial Pink Cap. Study schema and procedures are outlined below.

TIME	0*	12-84 hours #	7 ± 3 days	14 ± 3 days	44 ± 4 days
Physical Exam	x		x	x	X
Etanercept/Placebo	x		x	x	
PK	x	x	x	X	
Cytokines	x	x	x		
CBC^	x		x	x	X
CRP	x		x	x	X
ESR	x				
Echo	x			x	X
EKG	x			x	X
AST, ALT	x		x	x	
Albumin	x		x	x	X

* Time 0 or baseline is defined as time first dose of study drug is given. Time 0 or baseline labs are almost always done before the patient has consented to the study. These labs are optional unless the patient is qualifying into the study through supplementary lab data. In general, admission laboratory values used to confirm diagnosis of KD can be used for the study, provided that they were within 24 hours prior to initiating IVIG. If a time zero lab value is not drawn as part of the clinical course prior to the patient enrolling in the study, it will not be collected and will be recorded as missing data. After enrollment, coordinators should try to retrieve extra serum obtained along with admission laboratory studies. This serum can be used for baseline pharmacokinetic assay, PK.

An EKG is normally done at time zero as part of clinical care. This EKG is optional, if an EKG is not performed at baseline it will not be recorded as a protocol deviation.

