6.4 Visit 4 (Day 14 ± 72 hours)- Clinic

A physical exam and a blood draw (approximately 7 cc) are required. A numbing agent may be used to decrease the discomfort associated with phlebotomy or study drug administration. The blood sample is sent to the laboratory for the tests listed in the schema while study personnel will process the PK sample and store for later shipping. An Echo and EKG are performed. A nurse administers a subcutaneous injection of study drug at the appropriate dosage.

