6.5 Visit 5 (Day 44 ± 4 days)- Clinic

A physical exam and a blood draw (approximately 7 cc) are required. . The blood sample is sent to the laboratory for the tests listed in schema. An Echo/ EKG is performed. No study drug is administered.

6.6 Treatment for refractoriness to IVIG.

All patients who fit the requirements for refractoriness to IVIG (see section 3.1) will receive standard clinical treatment as determined by the attending physician. Standard treatment is usually a second dose of IVIG, and is defined in the American Heart Association guidelines. Retreatment with IVIG will not interrupt the study and study medication should still be administered.

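### Adverse events are to be reported to 30 days after the last dose, but the last scheduled visit is timed from the first dose and can fall up to 7 days before that period ends (minor)

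*Combined protocol and SAP*

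**What the plan says.** **Reporting period.** Section 8.1 runs adverse event reporting from the start of any study procedure to the end of follow-up, and "the study treatment follow-up is defined as 30 days following the last administration of study treatment". Section 8.2 requires all adverse events in the study period to be recorded and has the investigator ask about them at each contact.

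**Clock for the visits.** The footnote to the schedule in Section 6 says "Time 0 or baseline is defined as time first dose of study drug is given". The third dose belongs to "6.4 Visit 4 (Day 14 ± 72 hours)- Clinic", where "A nurse administers a subcutaneous injection of study drug at the appropriate dosage". The last visit is "6.5 Visit 5 (Day 44 ± 4 days)- Clinic", at which no study drug is given. Nothing links its date to the actual date of the third dose.

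**Final-dose window.** The schedule and Section 6.4 allow 3 days either side of day 14. Section 3.3 says "we will give the final dose at $14 \text{ days} \pm 2$ in order to maintain levels at least 3 weeks".

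**After Visit 5.** Section 8.1 has the investigator ask families at the last visit to report later events that they or their physician think could be related to the study. Sections 6 and 6.1 also ask parents to tell the coordinator of any sign of infection, with no end date given. The echocardiogram surveillance in Section 6.6 covers only children with a positive echo at Visit 5 and collects visit notes and imaging reports.

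**Safety endpoint.** Section 3.2 counts the "number of adverse events, serious or otherwise within 30 days of treatment", with specific focus on serious infections. It does not say whether the 30 days run from the first dose or the last. Section 7 compares adverse event rates by Poisson or negative binomial regression and states neither a counting window nor an exposure term.

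**The concern.** The reporting period is tied to the last dose and the closing visit to the first dose, and both the third dose and the closing visit have windows. A child dosed late and seen early has the closing visit before the reporting period ends. For the remaining days no contact with all children is scheduled at which adverse events are actively sought, although Section 8.1 still requires all of them to be reported.

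Secondary Aim 1 compares the safety profile between arms. What is at stake is whether the event counts cover the period the protocol defines, and cover it equally from child to child. The missing anchor in Section 3.2 adds a second uncertainty: two analysts could count the same endpoint over different periods.

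**Working it through.** **Inputs**
- Time 0 = first dose (Section 6, schedule footnote).
- Third dose on day d = 14 ± 3, so d = 11 to 17 (schedule; Section 6.4). Under Section 3.3, d = 14 ± 2, so d = 12 to 16.
- Visit 5 on day v = 44 ± 4, so v = 40 to 48, which is 9 whole days (schedule; Section 6.5).
- Reporting period ends on day d + 30 (Section 8.1).

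**Nominal timing.** 14 + 30 = day 44, which is the stated Visit 5 day. The gap is zero.

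**Extremes.** Shortfall = (d + 30) − v.
- Section 6.4 window: 17 + 30 − 40 = 7 days, leaving 40 − 17 = 23 days observed after the last dose.
- Section 3.3 window: 16 + 30 − 40 = 6 days.
- In the other direction, 48 − (11 + 30) = 7 days of observation beyond the period.

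**How often and how much, Section 6.4 window.** Assume each whole day in each window is equally likely and independent. The documents do not say this; it is for illustration. For a given d there are d − 10 Visit 5 days before the period ends.

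| Third dose (day) | Period ends (day) | Visit 5 days too early, of 9 | Sum of shortfalls (days) | Visit 5 days left if anchored |
|---|---|---|---|---|
| 11 | 41 | 1 | 1 | 8 |
| 12 | 42 | 2 | 3 | 7 |
| 13 | 43 | 3 | 6 | 6 |
| 14 | 44 | 4 | 10 | 5 |
| 15 | 45 | 5 | 15 | 4 |
| 16 | 46 | 6 | 21 | 3 |
| 17 | 47 | 7 | 28 | 2 |
| Total | | 28 of 63 | 84 | mean 35/7 = 5 |

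- Share that fall short: 28/63 = 44%.
- Mean shortfall over all combinations: 84/63 = 1.3 days, or 1.33/30 = 4.4% of the period.
- Mean shortfall among those that fall short: 84/28 = 3 days.
- Shortfall of 4 days or more: 1 + 2 + 3 + 4 = 10 of 63 (16%). Shortfall of 7 days: 1 of 63 (1.6%).

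**Section 3.3 window** (rows 12 to 16). Share 20/45 = 44%; mean shortfall (3 + 6 + 10 + 15 + 21)/45 = 55/45 = 1.2 days.

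**Early stoppers.** A child whose last dose is the second receives it by day 7 + 3 = 10, so the period ends by day 40 and a Visit 5 held in its window is never early.

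**Drug level in the days at issue.** Section 1.4 gives a median half-life of 115 hours. In the worst case the unobserved days begin 23 days after dosing: 23 × 24 / 115 = 4.8 half-lives. With simple first-order decay (an assumption), 0.5^4.8 is about 4%.

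**Two readings of Section 3.2.** From the last dose, the endpoint closes on days 41 to 47, as in Section 8.1. From the first dose it closes on day 30, which is 30 − 17 = 13 to 30 − 11 = 19 days after the third dose.

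**The case against.** The strongest reply is that the plan is aligned as designed and that the gap is only the slack of ordinary visit windows, which also work the other way. The reporting duty in Section 8.1 does not stop at Visit 5, families are told to report later events, and parents are asked to report any sign of infection whether or not it seems related. The safety focus is infection needing hospital admission, which is unlikely to go unnoticed. Most of this stands, and it limits the point to a minor one. What remains is that a duty to report is not a contact at which events are sought. The instruction given at the last visit reaches only events thought related, and the infection instruction is passive and covers one type of event. Section 8.2 also breaks off mid-sentence on serious events after the study period, so the full text on late events cannot be checked.

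A reader might infer more than the documents support:
- *That a large part of safety follow-up is lost.* Seven days of 30 is 23%, but it is one extreme combination; the illustrative mean is 4.4%.
- *That the missed days fall while the drug is still active.* At worst they start about 4.8 half-lives after dosing, and Section 3.3 aims to maintain levels for at least 3 weeks, not to day 40.
- *That the comparison between arms is biased.* Both arms are randomized, blinded and share one schedule; nothing shows a differential effect.
- *That event rates must be understated.* That depends on whether unobserved days stay in the denominator. Section 7 does not state the exposure term, so it is possible but not established.
- *That Section 3.2 contradicts Section 8.1 by closing the endpoint on day 30.* Section 3.2 names no anchor, treatment is a three-dose course, and read with Section 8.1 the two are consistent. It is an ambiguity.

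**Conclusion.** The point holds as a minor one. Visit 5 can precede the end of the reporting period by up to 7 days under the Section 6.4 dose window, or 6 days under Section 3.3, and no later contact with all children is scheduled. These maxima follow from the stated windows alone. The 44% share and the 1.3-day mean rest on the even-spread assumption and would change with actual booking practice; if sites keep to nominal days, there is no gap. The consequence is modestly incomplete and uneven capture of adverse events, mainly those not believed related, with no evident bias between arms. Section 3.2 needs clarifying because its unanchored window allows the endpoint to be read as ending about two weeks before the reporting period does.

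**What to change.** 1. **Section 6.5 and the schedule.** Keep days 40 to 48 and add *and not earlier than 30 days after the actual last dose*. This always fits, because the period ends by day 47. Where Visit 5 has to be earlier, make a safety phone call at 30 days after the last dose.
2. **Section 3.2.** Replace the unanchored 30-day wording with *during the reporting period defined in Section 8.1 (to 30 days after the last dose)*. Pointing to Section 8.1 is safer than writing *from the first dose*, because the Section 8.1 period starts earlier, with the first study procedure.
3. **Sections 3.3 and 6.4.** Reconcile the two final-dose windows. This review does not say which is right.

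**Cost.** The wording changes are short and no visit is added. The real cost is booking: the Visit 5 window narrows from 9 days to between 2 and 8, with a mean of 5 if dose days are evenly spread. Visit 5 also carries the 6-week echo, so a tight window after a late third dose may produce out-of-window visits. The phone call avoids this, at the price of one extra contact for the children concerned.

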The American Academy of Pediatrics and the American Heart Association have published guidelines for epidemiological case definition. KD treatment, including IVIG and aspirin, is recommended for patients fitting these criteria. Generally, supportive laboratory data also exist including elevation of erythrocyte sedimentation rate and C reactive protein (CRP > 3.0 , although usually much higher). Thrombocytosis (platelet count $> 500,000$) usually occurs in the second week.

- Patients in this study (age 2 months to 20 years) will fit the standard epidemiological definition of acute KD as recommended by the joint AHA/AAP guidelines or fit criteria for diagnosis of incomplete KD as described below. Patients will be enrolled only after a clinical decision to treat with IVIG has been made by the treating physician.
- Patients may be enrolled if they begin IVIG infusion within 10-13 days of onset of illness with day 1 defined as the first day of fever. A patient may be enrolled with greater than 10 days of fever upon written approval or email confirmation from the study Principal Investigator ([name]) on a case by case basis.
- Parents of subject or non-minor subject must be able and willing to give written informed consent and comply with the requirements of the study protocol and must authorize release and use of protected health information.

Patients will fit American Heart Association, American Academy of Pediatric guidelines for diagnosis of Kawasaki Disease

Fever persisting at least 5 days†

Presence of at least 4 principal features:

- 1) Changes in extremities
Acute: Erythema of palms, soles; edema of hands, feet
Subacute: Periungual peeling of fingers
- 2) Polymorphous exanthem
- 3) Bilateral bulbar conjunctival injection without exudate
- 4) Changes in lips and oral cavity: Erythema, lips cracking, strawberry tongue, diffuse injection of oral and pharyngeal mucosae
- 5) Cervical lymphadenopathy (1.5-cm diameter), usually unilateral

Patients with fever at least 5 days and 3 principal criteria can be diagnosed with Kawasaki disease when coronary artery abnormalities are detected by 2 dimensional echocardiography (see section on Echocardiography). A qualifying echocardiogram is defined as coronary artery z score ≥ 2.5 in the proximal coronary artery or left anterior descending, or aneurysm by Japanese Ministry of Health criteria.

CONFIDENTIAL

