 - l. Severe comorbidities (diabetes mellitus requiring insulin, CHF of any severity, MI, CVA or TIA within 3 months of screening visit, unstable angina pectoris, uncontrolled hypertension (sitting systolic BP > 160 or diastolic BP \geq 100 mm Hg), oxygen-dependent severe pulmonary disease, history of cancer within 5 years [other than resected cutaneous basal or squamous cell carcinoma or in situ cervical cancer])
 - m. Exposure to hepatitis B or hepatitis C or high risk factors such as intravenous drug abuse in patient's mother, or history of jaundice (other than neonatal jaundice).* SLE, history of multiple sclerosis, transverse myelitis, optic neuritis or chronic seizure disorder.

CONFIDENTIAL

This material is the property of the Seattle Children's Research Institute. Do not disclose or use except as authorized in writing by the study sponsor-investigator.

- n. Use of a live vaccine (Measles Mumps Rubella or Varicella) 30 days prior to or during this study with the exception that a patient who has received Influenza mist vaccine may be enrolled after 14d from administration of the vaccine.
- o. Any condition judged by the investigator to cause this clinical trial to be detrimental to the patient
- p. History of non-compliance with other therapies
- q. Must not have received immunosuppressive agents for at least three months prior to enrollment.

*Note, liver enzymes, AST or ALT are frequently elevated in KD, and will not be used as an exclusion.

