Adverse events will be tabulated for each treatment group by severity, relationship to study drug and body system affected (according to the NCI CTC grading and MEDDRA classification system). The outcome of any SAE episodes that occur will be summarized. Adverse event rates will be compared between treatment groups using Poisson or negative binomial regression modeling. The proportions of subjects experiencing an adverse event of any type and the proportions experiencing an SAE will be compared using chi-square or Fisher's Exact testing.

Pharmacokinetic analyses: PK analyses will be performed after completion of the study and unblinding, so as not to unblind study investigators. Samples from patients receiving etanercept will be forwarded to the Seattle site for storage and then later submitted to Amgen for determination of serum drug concentrations. Peak and trough analyses will be performed. Drug clearance, volume of distribution and $\frac{1}{2}$ life will be determined using etanercept modeling and algorithms⁴¹ and loaded on SAAM2 software available at the University of Washington.

CRP and other standard laboratory studies will be performed in the clinical laboratory of each participating hospital. Serum cytokines, IL-3, IL-6, and TNF α will be performed in Center of Developmental Therapeutics at Children's Hospital Research Institute in Seattle. Assay will be performed on Luminex-200 multiplex system, which resides in center.

8 Safety and Adverse Events

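### Section 8.1 has two unreconciled rules for when an abnormal result is an adverse event; the laboratory rule lets Kawasaki findings dilute the any-AE and AE-rate comparisons

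*Combined protocol and SAP*

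**What the plan says.** All of this is in the combined protocol and SAP.

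- **Section 8.1, Adverse Event.** "Abnormal results of diagnostic procedures are considered to be adverse events if the abnormality" leads to withdrawal, accompanies an SAE or clinical signs, prompts treatment or further tests, or is judged clinically significant. The general definition covers events that arise or worsen during the study.
- **Section 8.1, Abnormal Laboratory Values.** "A clinical laboratory abnormality should be documented as an adverse event if any one of the following conditions is met". The first condition is "The laboratory abnormality is not otherwise refuted by a repeat test to confirm the abnormality". The second is "The abnormality suggests a disease and/or organ toxicity". The third is a need for active management.
- **Section 8.1, Expected Adverse Events.** The list includes "Lab abnormalities; elevated CRP and ESR; thrombocytosis, hypoalbuminemia, anemia, pyuria, elevation of liver transaminases", alongside many clinical findings of the disease.
- **Section 4.1.** Thrombocytosis "usually occurs in the second week". The Section 4.2 footnote adds that "liver enzymes, AST or ALT are frequently elevated in KD, and will not be used as an exclusion".
- **Section 6 schedule.** CBC, CRP and albumin are taken at days 7, 14 and 44, and AST and ALT at days 7 and 14. Most baseline laboratory values are optional and may be recorded as missing.
- **Section 7.** "The proportions of subjects experiencing an adverse event of any type and the proportions experiencing an SAE will be compared" by chi-square or Fisher's exact test, and AE rates by Poisson or negative binomial regression. These serve Secondary Aim 1 in Section 2.

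**The concern.** The laboratory conditions are alternatives, so the first is enough by itself. A value confirmed on repeat meets it and, read literally, so does a value that nobody repeated. The second condition also admits Kawasaki values, because they do suggest a disease. Nothing says which of the two lists governs a laboratory result. Two sites could each follow the text and report quite different numbers of AEs for the same child.

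Section 8.1 exempts most hospitalization for the target disease from AE reporting but has no parallel exemption for the disease's laboratory findings; it names them as expected AEs, and Section 8.2 requires all AEs to be recorded.

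The yes/no any-AE comparison is the most exposed. A child already counted because of a disease-related laboratory value cannot be counted again for a drug-related event, so the difference between arms shrinks as the shared background grows.

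**Working it through.** **1. Does a Kawasaki laboratory value qualify?** Take thrombocytosis in a child enrolled in the first week of illness with a normal baseline platelet count.
- General definition: the finding is new during the study, so it is not excluded.
- General list: with no symptom, treatment, extra test or judgement of significance, it meets no criterion.
- Laboratory list: a raised count on the scheduled CBC that is not refuted meets the first condition. It is an AE.

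The same value is therefore an AE under one list and does not meet the other. A value already abnormal at entry and improving can be read as outside the general definition, but the laboratory rule does not repeat that limit. Where the baseline is missing, it cannot be applied.

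**2. Effect on the any-AE proportion.** The plan states no rate, difference or power for any AE comparison, so there is no figure of its own to reproduce. Inputs:
- n = 98 per arm, from 196 subjects with 1:1 allocation assumed.
- Two-sided 5% level: assumed.
- Non-laboratory AE rates p of 40% and 60%: assumed.
- Share b of children with a disease-driven laboratory AE, equal in both arms and independent of other AEs: assumed at 0, 50%, 80% and 90%.

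Any-AE proportion = 1 − (1 − p)(1 − b), so the difference is d = 0.20 × (1 − b).

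Power = Φ[(d − 1.96 s0)/s1], with s0 = √(2p̄(1 − p̄)/n), where p̄ is the mean of the two proportions, and s1 = √([p1(1 − p1) + p2(1 − p2)]/n).

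| b | any-AE rates | d | s0 | s1 | power |
|---|---|---|---|---|---|
| 0 | 40% vs 60% | 0.20 | 0.0714 | 0.0700 | 80% |
| 50% | 70% vs 80% | 0.10 | 0.0619 | 0.0614 | 36.5% |
| 80% | 88% vs 92% | 0.04 | 0.0429 | 0.0428 | 15% |
| 90% | 94% vs 96% | 0.02 | 0.0311 | 0.0311 | 9% |

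Example for b = 50%: (0.10 − 1.96 × 0.0619)/0.0614 = −0.35, and Φ(−0.35) is about 0.365. Using s1 in place of s0 gives 37.0%, so I quote about 37%.

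The Primary Aim in Section 2 speaks of 110 per group. At n = 110 the same formula gives 85%, 40%, 17% and 10%.

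**3. Other assumed rates.** With 20% vs 40% and 98 per arm, chi-square power is 87% at b = 0, then 31%, 12%, 8% and 6% at b = 50%, 80%, 90% and 95%. Fisher's exact test gives 84%, 26%, 9%, 5% and 2%.

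**4. Effect on AE rates.** Assume Poisson means of 0.5 and 1.0 non-laboratory events per child, and add m laboratory events per child in both arms. Power = Φ[ln(λ1/λ0)/SE − 1.96], with SE = √(1/(98λ0) + 1/(98λ1)).

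| m | rate ratio | power |
|---|---|---|
| 0 | 2.00 | 98% |
| 1 | 1.33 | 75% |
| 2 | 1.20 | 56% |
| 3 | 1.14 | 44% |
| 5 | 1.09 | 31% |

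The starting effect differs from step 2, so the two tables are not like for like. The structural difference is that the absolute excess of 0.5 events per child survives in a count and only the noise grows, whereas in the yes/no measure the excess itself shrinks by the factor 1 − b.

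**The case against.** The case for leaving the text alone has real substance.

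- **Safety does not rest on the any-AE proportion.** Section 7 also tabulates AEs by severity, relationship and body system and compares SAE proportions separately. Section 3.2 makes serious infections the specific focus, and Section 8.5.1 has the DMC concentrate on infections. A reader might infer that the trial cannot show a drug safety difference; the documents do not support that. For example, assumed SAE rates of 5% vs 20% give 89% power at 98 per arm, and the laboratory rule hardly touches them. This stands.
- **The rule does not reach every abnormal value.** CRP, anemia, albumin and ALT can support the entry diagnosis (Section 4.1), so many will be abnormal at baseline, and the new-or-worsening requirement and the preexisting-condition definition limit what counts. IVIG may start as late as days 10 to 13 of illness, so some children may have thrombocytosis at entry. It would therefore be wrong to infer that almost any abnormal Kawasaki value becomes an AE. This stands for values known to be abnormal and improving, not for new, worsening or baseline-unknown ones.
- **Grouping.** Section 8.2 groups clearly related findings under one diagnosis. That lowers event counts. It does not by itself change whether a child has any AE, unless the grouped diagnosis is taken to be the preexisting Kawasaki disease.
- **The lists are not strict opposites.** The general list says when a result is an AE, not that nothing else can be. So they differ and are unreconciled, rather than flatly contradictory.
- **Laboratory values are not the only source.** Fever, rash, peeling and other clinical findings are also expected AEs and would fill the any-AE category by themselves. This stands and shapes the fix.
- **Site forms.** The AE forms are listed as attachments but are not in the text available, so recording instructions there cannot be judged.

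A reader might also infer that laboratory AEs, by tracking inflammation, would fall under an effective drug and offset a real harm. That is plausible, but the documents give nothing to quantify it, and the illustrations assume equal laboratory rates in both arms.

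**Conclusion.** The point holds as a defect of definition with a limited analytical consequence. Section 8.1 leaves two rules in force, and the laboratory rule can be met by an unrefuted value with no clinical relevance. Following it adds disease findings to both arms, weakens the any-AE comparison most and the AE-rate comparison less, and invites inconsistent reporting between sites.

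The direction follows from the text; the size does not. It depends on assumed non-laboratory AE rates, an assumed share of children with laboratory AEs, equality between arms and independence. Under the 40% vs 60% illustration, power is about 37% at a 50% background and 9% at 90%. Complete loss of the comparison would need nearly every child to have a disease-driven AE, which the documents do not establish.

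**What to change.** Reword Section 8.1 so that a laboratory abnormality is an AE only if all three of these hold:
1. it is not refuted by a repeat test;
2. it is new or worsened from baseline, with a stated rule for a missing baseline;
3. it meets one of the criteria in the general list for abnormal diagnostic results.

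State that other expected Kawasaki laboratory values stay in the laboratory dataset, and summarise them by arm.

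Rewording alone may not be enough, because some disease-related values will meet a general criterion, such as accompanying clinical signs, and expected clinical findings remain. In Section 7, therefore, also report the any-AE and AE-rate comparisons excluding the expected Kawasaki findings, clinical and laboratory, listed in Section 8.1. This should supplement the full comparison, not replace it: the list includes hypersensitivity, for example, which could also be a drug effect.

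The cost is a few sentences in Sections 8.1 and 7, an instruction on the case report form and one additional version of each comparison. Fewer minor laboratory AEs would be listed, but every value is still collected and summarised.
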